Patient behavior is affected by caregiver responses, and caregiver responses are in turn influenced by both patient behavior and the historical context of their relationship [10, 14, 18, 7]. Critical and hostile responses on the part of the caregiver are associated with increases in patient dementia symptoms [8]; thus, if we can reduce caregiver's frustration and criticism, we expect this will reduce escalation of negative interactions, reduce caregiver burden and stress over time, and in turn decrease patient stress and physiological reactivity. We will assess the quality of the caregiver-patient relationship and caregiver stress and burden before beginning the study.

7) *Family Assessment Device*: The FAD is a self-report measure that is given as a set of seven subscales of varied length. Each subscale measures a different dimension of family function. Scores for each dimension (problem solving, communication, roles, affective responsiveness, affective involvement, behavior control, and general functioning) are calculated separately as the mean of the items in that subscale. The information obtained through the FAD allows for the elucidation of the structure and organization of the family system, as well as the identification of common patterns of interaction among family members. The FAD is heavily used in research related to the function of family systems, and it has demonstrated excellent validity and reliability in both non-clinical and clinical populations [39].

8) *Caregiver Emotion Regulation and Mindfulness*: The 16-item, Difficulties in Emotion Regulation Scale (DERS-16) will be used to measure caregivers' ability to regulate emotions at baseline and end of study. The scale used is the brief version of a theoretically-driven, valid, and reliable self-report tool used to measure difficulties with emotion regulation. The brief version will be more easily administered with the study population and has been shown to be valid and reliable [41]. Additionally, caregivers will be asked to complete the 39-item Five Facet Mindfulness Questionnaire to measure their capacity for five different domains of mindfulness practice at baseline and end of study. The five facets include non-reactivity to the inner experience, non-judgment of the inner experience, acting with awareness, observing, and describing internal states. The questionnaire has good reliability and validity [42].

D. Detailed study procedures

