Visit 1: The study information brochure and the study consent forms will be reviewed in person, via video call, or via telephone with the potential study participants. Written, informed consent will be obtained for both the family caregiver and the persons with dementia. If informed consent is unable to be obtained for the person with dementia based upon their scores on the Capacity to Consent instrument, their surrogate decision-maker will provide informed consent and assent for the person with dementia will be ascertained by the study team member. If willing, participants will be asked to sign for consent electronically using a REDCap link sent via email. In REDCap participants will provide electronic signatures on the consent form indicating they agree to participate in this study. Following the consenting procedure, the acoustic monitor (microphone) and accompanying laptop computer (for transferring the acoustic data to the Cloud for translation processes to occur) will be placed in the participant's home at the location that is amenable to the study participants. We anticipate this will be the kitchen/dining area and the living room areas of the home as many interactions occur in these locations. No acoustic monitoring will occur in any areas of the house that they do not wish to have a microphone placed. A 5-minute audio

recording will be obtained from the caregiver and person with dementia. The recording will be uploaded to the recommender system to generate a person ID for vocal recognition during the study.

The acoustic monitoring will occur for up to 1 month to establish baseline interactions between the family caregiver and the persons with dementia. A Smart Phone will be given to the caregiver for use during the study period for the purpose of receiving recommendations and providing feedback through daily and weekly online surveys. Written and verbal instructions on the use of the acoustic monitoring and the Smart Phone will be provided to study participants. There are no steps that participants need to follow to maintain the equipment, other than keeping the microphone and laptop plugged in to an electric outlet and recharging the Smart Phone. We will also ensure the internet connection via Wifi is enabled.

The following surveys will be administered via paper and pencil forms or RedCap to the family caregiver:

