2. TICS

During Visit 1, research personnel will prompt the family caregiver to establish an emergency plan. This plan is meant to reinforce use of previously established procedures or create procedures to be used in the event of an emergency. Research personnel will stress that the study equipment is not monitored and is not capable of contacting emergency services and should not be used for such activity. Examples of an emergency plan could include, but are not limited to, notifying a healthcare provider, calling 911, or calling another family member. Caregivers will be reminded periodically to follow the procedures of their emergency plan in the event of any emergency.

We anticipate Visit 1 will take between 90-135 minutes.

Between visits 1 and 2, participants will complete a short survey about their experience deploying the study equipment in their home. The questionnaire will take about five to ten minutes to complete.

Visit 2: Upon completion of the first two weeks to one month of baseline data collection, the trained Graduate Research Assistant will visit the study participants in their homes or set up a

virtual meeting via Zoom or telephone to educate the participants regarding the text messages they will be receiving from the study team when stressful situations are identified. The Graduate Research Assistant will also train caregivers on how to perform mindfulness-based activities. A standardized training guide will be used for all participants by the trained GRAs. During the visit, a principal investigator (PI) may monitor whether the stress management education is delivered as intended (i.e., intervention fidelity check) with no recordings. Retraining of GRAs may be performed based upon the results of fidelity checks. Caregivers will be asked to select personal preferences for messages and helpful reminders they will receive in the text messages that would prompt their understanding of the text messages received from a pre-set list of choices. Additionally, family caregivers will be taught to respond to the daily and weekly feedback surveys regarding their use of the text messages.

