Importance of the Knowledge to Be Gained. There may be immediate benefit to the subjects participating in the study, although we do not guarantee this, as family caregivers will be given specific knowledge and helpful reminders to mitigate potentially problematic behaviors regarding care of their loved one with ADRD. If successful, the knowledge gained will be important because of its substantial potential to enhance the treatment of difficult to manage, prevalent, and burdensome care problems of persons with ADRD, increasing their quality of life, reducing caregiver burden, delaying or reducing institutionalization, and decreasing the costs of caring for persons with AD in the future.

E. Internal Validity

The purpose of this study is primarily to establish feasibility and test the model. If we can establish that our system reduces emotional reactivity and that patient and caregiver self-reported and observed outcomes improve over time compared to an individualized baseline period, we will have established justification for a more comprehensive design that will more fully test this system against a credible alternative.

Thus, the caregivers will fill out the measures provided to them and then their interactions with the patients will be monitored for a month to establish a baseline of functioning. We will assess levels of reactivity during caregiver-patient interactions and the time it takes for them to return to their own baseline. At the end of the one-month assessment period, the caregiver will be brought in for training on the recommendations, after which they will receive recommendations when the system detects emotional reactions when the caregiver and patient are with each other. The recommendations will be personalized over time. Effectiveness of the recommendations will be assessed by examining whether the recommendations reduce the frequency and intensity of the negative patient-caregiver interactions and the time required for reactivity to return to baseline in real time, as assessed by information recorded by the monitoring system. Effectiveness also will be assessed by monitoring change in the self-report measures during the baseline period compared to the period in which the caregiver is receiving the recommendations.

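### The promised baseline-period versus recommendation-period comparison of self-report change cannot be made, because no outcome scale is scheduled at the end of the baseline period

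*Protocol*

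**What the plan says.** Section E states the comparison: "Effectiveness also will be assessed by monitoring change in the self-report measures during the baseline period compared to the period in which the caregiver" (the sentence ends by naming the recommendation phase). The same section makes it part of the case for a larger trial that "patient and caregiver self-reported and observed outcomes improve over time compared to an individualized baseline period".

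The timing of the scales is set in three places:

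- Section E gives the order: "the caregivers will fill out the measures provided to them and then their interactions with the patients will be monitored for a month". The scales come first and the baseline period follows.
- Section C (Measurement/Instrumentation) says: "We will assess the quality of the caregiver-patient relationship and caregiver stress and burden before beginning the study". For the DERS-16 it schedules caregivers' "ability to regulate emotions at baseline and end of study", and it gives the Five Facet Mindfulness Questionnaire (FFMQ) the same two time points.
- Section D (Study Visits) introduces the Visit 1 list with "The following surveys will be administered via paper and pencil forms or RedCap to the family caregiver". The list holds the DASS, DERS-16, FFMQ, RMBPC, MCSI and FAD.

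Visit 2 takes place "Upon completion of the first two weeks to one month of baseline data collection" and consists of training and the choice of message preferences. Visit 3 reinforces training and deals with problems. Visit 4 collects the end-of-study measures without naming them.

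**The concern.** A change during the baseline period needs a score at its start and a score at its end. The schedule supplies the first and not the second, so for self-report the baseline period has no data of its own.

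The study openly has a single group, and the absence of a control is not the point here. The individualized baseline period is what section E offers in place of a control. If a Visit 1 to Visit 4 change is reported under the present wording, readers will take it for a comparison of two periods within the same caregiver, and that comparison was not made.

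There is a specific reason to care about the weeks before recommendations. Caregivers must score above a cut-off on the RMBPC to be eligible, and the RMBPC is also an outcome scale. Some fall after selection could occur without any intervention. The documents do not allow this to be sized.

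**Working it through.** The plan states no figure for this comparison, so there is none to reproduce. The check has three parts.

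**1. Every self-report collection in the protocol**

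| Time | What is collected | Outcome scale? |
|---|---|---|
| Screening | RMBPC cut-off for eligibility | Precedes Visit 1; not an end-of-baseline score |
| Visit 1 | DASS, DERS-16, FFMQ, RMBPC, MCSI, FAD | Yes, before the baseline period |
| Between Visits 1 and 2 | "Between visits 1 and 2, participants will complete a short survey about their experience deploying the study equipment in their home" | No |
| Visit 2 | Training, message preferences | No |
| After Visit 2 | Per-message, daily and weekly feedback on the texts | No, and nothing comparable in the baseline period |
| During the study | Practice worksheet | No |
| Visit 3 | Reinforcement, troubleshooting | No |
| Visit 4 | End-of-study measures | Yes; explicit only for DERS-16 and FFMQ |

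**2. Can the change be split?** Let B be the length of the baseline period in months, T the time of Visit 4, b the monthly change in the baseline period and r the monthly change under recommendations. Then

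score(t) = a + b·min(t, B) + r·max(t − B, 0).

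- Scores at Visits 1 and 4 only: the change is B·b + (T − B)·r, one equation in two unknowns. The design matrix has rank 2 of 3, and r − b is not estimable for B = 0.5 or 1 month.
- Adding a score at Visit 2: rank 3 of 3, and r − b is estimable.

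The share of the Visit 1 to Visit 4 interval that precedes recommendations uses a baseline of two weeks to one month (Visit 2), participation of up to four months (Study Visits), and three months of recommendations (Year Three timeline):

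- 0.5/4 = 12.5%
- 0.5/(0.5 + 3) = 14.3%
- 1/4 = 25%

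**3. What would a Visit 2 score buy?** Inputs: n = 30 dyads (section B) and t(29) = 2.045. The protocol gives no correlations, so I assume unit SD and equal correlations r between any two administrations of 0.9 to 0.7 (here r is a correlation, not the slope above).

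- *A single change* (for example Visit 2 to Visit 4). The 95% half-width is 2.045 × √(2(1 − r)/30). At r = 0.9 this is 2.045 × √(0.2/30) = 0.167 SD; at r = 0.7 it is 2.045 × √(0.6/30) = 0.289 SD.
- *The contrast between periods.* The periods differ in length, so the baseline-period change is scaled up by k = recommendation months / baseline months, assuming a linear trend: D = (V4 − V2) − k(V2 − V1). Its variance is (1 − r)[1 + (1 + k)² + k²], and the half-width is 2.045 × √(variance/30).

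| Baseline | Recommendations | k | Bracket | Half-width, r = 0.9 | Half-width, r = 0.7 |
|---|---|---|---|---|---|
| 1 month | 3 months | 3 | 26 | 0.602 SD | 1.043 SD |
| 2 weeks | 3 months | 6 | 86 | 1.095 SD | 1.897 SD |
| 2 weeks | 3.5 months | 7 | 114 | 1.261 SD | 2.184 SD |

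An extra administration therefore makes the contrast estimable, but only imprecisely at this sample size.

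**The case against.** The strongest reply is that the sentence is loose and means only scores at baseline against scores under recommendations. Section C treats the first DERS-16 and FFMQ administration as the baseline value, which fits that reading, and two administrations would then be enough. A Visit 1 to Visit 4 change is also a genuine within-person change, in a study that calls itself primarily a feasibility study. Finally, a free rewording suggests a small fault.

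Part of this stands. The pre-post change can be computed wherever the Visit 4 set includes the scale, and it is legitimate if labelled correctly. But the sentence speaks of change during one period compared with another period. Even on the looser reading, the Visit 1 score comes before the baseline weeks, so the change includes two weeks to one month without recommendations. A statistical analysis plan cannot repair this, because it cannot analyse a score that is never collected.

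Two further points are fair. Caregivers receive information on unmet needs at the first study visit, so the baseline weeks are not strictly untreated; this also applies to the acoustic baseline, although those data can still be split by period. And repeating only some scales at Visit 2 leaves the others without the promised comparison, so they would need the reworded text in any case.

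**Conclusion.** The concern holds. The protocol commits to a self-report comparison that its own schedule makes impossible, and the statement supports its effectiveness claim. It should be fixed.

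The finding that the change cannot be split rests on the schedule alone and needs no numerical assumption. The 12.5% to 25% range describes time, not bias; the size of any bias is unknown. The precision figures rest on the assumed correlations and, for the contrast, on a linear trend. The acoustic part of the case for a larger trial is not touched by this point.

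**What to change.** **Option 1, sufficient by itself.** Reword section E so that self-report is an uncontrolled change from Visit 1 to Visit 4 that includes the weeks before recommendations. Limit the claim of improvement against an individualized baseline period to the acoustic outcomes. This is a wording change with no cost to participants, and it works even if data collection is complete.

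**Option 2, only if the period comparison is wanted.** Repeat the RMBPC, MCSI and DASS at the existing Visit 2, before training.

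- Report Visit 2 to Visit 4 as the recommendation-period change with a 95% confidence interval, and state that it is still uncontrolled.
- Report Visit 1 to Visit 2 descriptively as the pre-recommendation change, and do not call it untreated.
- Claim no formal test of the contrast between periods.
- Keep the Option 1 wording for the FAD, DERS-16 and FFMQ.

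The cost is one more completion of three instruments (RMBPC 24 items, MCSI 13 items, and the DASS), assumed to take 15 to 20 minutes. The protocol itself names survey burden on caregivers as a risk, and the gain is limited by the precision shown above.

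Under either option, list the measures collected at Visit 4.
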